9.11.2.2. Analysis of Secondary and Exploratory Outcomes

Prevalence of the secondary and exploratory outcomes will be calculated according to the conventions described in [Table 9.7](#). In general, the prevalence of each outcome will be calculated by dividing the number of cases of the outcome by the appropriate denominator for that particular outcome, based on clinical knowledge.

Table 9.7. Calculation of Secondary and Exploratory Outcome Prevalence

Outcome [Exposure window]	Numerator	Denominator
Secondary outcomes		
Maternal pregnancy complications		
Gestational diabetes [Exposure: Any trimester]	Individuals with gestational diabetes	Individuals included in the analysis population
Sensitivity analysis: Gestational diabetes	Gestational diabetes among pregnancies with pregnancy outcome data	Individuals with pregnancy outcome data
Pregnancy-induced hypertension [Exposure: Any trimester]	Individuals with pregnancy-induced hypertension	Individuals with pregnancy of 20 gestational weeks or more
Sensitivity analysis: Pregnancy-induced hypertension	Pregnancy-induced hypertension among pregnancies with pregnancy outcome data	Individuals with pregnancy of 20 gestational weeks or more with pregnancy outcome data
Pre-eclampsia [Exposure: Any trimester]	Individuals with pre-eclampsia	Individuals with pregnancy of 20 gestational weeks or more
Sensitivity analysis: Pre-eclampsia	Pre-eclampsia among individuals with pregnancy outcome data	Individuals with pregnancy of 20 gestational weeks or more and with pregnancy outcome data
Eclampsia [Exposure: Any trimester]	Individuals with eclampsia	Individuals with pregnancy of 20 gestational weeks or more
Sensitivity analysis: Eclampsia	Eclampsia among individuals with pregnancy outcome data	Individuals with pregnancy of 20 gestational weeks or more with pregnancy outcome data
Fetal Outcomes		
SAB [Exposure: DOC to $\leq 19^{6/7}$ gestational weeks]	SABs among individuals with pregnancy outcome data who are enrolled (and exposed, if applicable) prior to 20 gestational weeks	Individuals with pregnancy outcome data who are enrolled (and exposed, if applicable) prior to 20 gestational weeks
Induced abortion [Exposure: Any trimester]	Individuals with pregnancy ending in induced abortions	Individuals included in the analysis population
Sensitivity analysis: Induced abortion	Induced abortions among individuals with pregnancy outcome data	Individuals with pregnancy outcome data
Stillbirth [Exposure: Any trimester]	Individuals with pregnancy ending in stillbirth	Individuals included in the analysis population
Sensitivity analysis: Stillbirth	Stillbirths among individuals with pregnancy outcome data	Individuals with pregnancy outcome data
Infant Outcomes		
Minor congenital malformations [Exposure: Any Trimester]	Live births with minor congenital malformations among individuals with pregnancy outcome data	Live births among individuals with pregnancy outcome data
Preterm birth [Exposure: DOC to < 37 weeks gestation]	Singleton preterm live births without MCMs among individuals with pregnancy outcome data who are enrolled (and exposed, if applicable) prior to 37 gestational weeks	Singleton live births without MCMs among individuals with pregnancy outcome data who are enrolled (and exposed, if applicable) prior to 37 gestational weeks

Outcome [Exposure window]	Numerator	Denominator
SGA [Exposure: Any trimester]	Singleton live births who are SGA at birth among individuals with pregnancy outcome data	Singleton live births among individuals with pregnancy outcome data
Sensitivity analysis: SGA	Singleton live births without MCMs who are SGA at birth among individuals with pregnancy outcome data	Singleton live births without MCMs with weight data among individuals with pregnancy outcome data
Postnatal growth and development outcomes		
Postnatal growth deficiency (at 4 and 12 months) [Exposure: Any trimester]	Singleton infants with postnatal growth deficiency based on weight/length/head circumference among infants with weight/length/head circumference data at the time point	Singleton infants with follow-up data at the time point
Sensitivity analysis: Postnatal growth deficiency (at 4 and 12 months)	Singleton infants without MCMs who were not born preterm or SGA with postnatal growth deficiency based on weight/length/head circumference among infants with weight/length/head circumference data at the time point	Singleton infants without MCMs who were not born preterm or SGA with weight/length/head circumference data at the time point
Infant developmental delay (at 4 and 12 months) [Exposure: Any trimester]	Singleton infants with developmental delay in a particular category among infants with developmental milestone data for the category at the time point	Singleton infants with follow-up data at the time point
Sensitivity analysis: Infant developmental delay (at 4 and 12 months)	Singleton infants without MCMs who were not born preterm or SGA with developmental delay in a particular category among infants with developmental milestone data for the category at the time point	Singleton infants without MCMs who were not born preterm or SGA with developmental milestone data for the category at the time point
Exploratory outcomes		
Hyperemesis gravidarum [Exposure: Any trimester]	Hyperemesis gravidarum	Individuals included in the analysis population
Inadequate gestational weight gain [Exposure: Any trimester]	Inadequate gestational weight gain	Individuals included in the analysis population
Maternal cardiac disease [Exposure: Any trimester]	Cardiac disease	Individuals included in the analysis population
LGA [Exposure: Any trimester]	Singleton live births at birth who were born LGA among individuals with pregnancy outcome data	Singleton live births among individuals with pregnancy outcome data
Rapid infant weight gain [Exposure: Any trimester]	Singleton live births without MCM who were not born preterm or SGA with rapid weight gain among infants with at least two recorded weight measurements	Singleton infants without MCMs who were not born preterm or SGA with at least two recorded weight measurements

Abbreviations: LGA = large for gestational age; MCM = major congenital malformation; SAB = spontaneous abortion; SGA = small for gestational age

For most outcomes, the analysis population (denominator) will be the number of pregnant individuals, number of pregnant individuals with pregnancy outcome data, the number of live births, or the number of infants with follow-up data at the specified time points, as appropriate; however, for some outcomes, the analysis population (denominator) will be restricted based on certain relevant factors:

- For live birth and infant outcomes (i.e., preterm birth, SGA, LGA, postnatal growth deficiency, rapid infant weight gain, and infant developmental delay), prevalence will be calculated among live births/infants excluding MCMs and multiple gestation pregnancies due to the higher risk of these outcomes among infants in these groups.
- For postnatal growth deficiency, rapid infant weight gain, and infant developmental delay infants born preterm, or SGA will be excluded from the main analysis population (denominator) due to different growth trajectories.
- For SAB and preterm birth, prevalence will be calculated among the subset of individuals who are enrolled in the registry prior to 20 and 37 gestational weeks, respectively. Additionally, for these time-to-event outcomes, data will be censored at appropriate time points: 20 gestational weeks for SAB and 37 gestational weeks for preterm birth.
- For pregnancy complications prevalence will be calculated according to the following assessment windows:
 - Pregnancy induced hypertension reported for the first time among participants after 20 weeks gestation.
 - Pre-eclampsia/eclampsia reported among participants after 20 weeks of gestation.
 - New-onset gestational diabetes reported among participants at any time during pregnancy
 - Inadequate maternal weight gain reported among participants at any time during pregnancy.
 - HG reported among participants anytime during pregnancy.
- Prevalence will be calculated at multiple time points for postnatal growth deficiency, rapid infant weight gain, and infant developmental delay will be assessed at 4 months (± 2 weeks) and 12 months (± 2 weeks) of infant age. At each time point, prevalence will be calculated among infants with data available for the particular outcome at that time point. If there is no assessment available at 4 and/or 12 months, available data will be evaluated based on the actual time of assessment (e.g., if the infant was measured at 6 months, these data will be compared to the values appropriate for a 6-month-old infant based on the growth charts). However, only development at 4 and 12 months will be reported as study outcomes, results from other time points will be reported in a separate category.

The unweighted univariate regression will be used to compare the crude (unadjusted) RRs for all outcomes. Adjusted methods will incorporate weights estimated using the IPTW method to balance the cohorts with regard to observable covariates (Section 9.11.2.4). A weighted generalized linear model using a binomial family and a log (relative risk) link will be employed to estimate an adjusted relative risk.

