- ^g Overweight defined as BMI ≥ 27 kg/m² and at least one weight-related comorbid condition (e.g., hypertension, dyslipidemia, type 2 diabetes mellitus, obstructive sleep apnea, or cardiovascular disease).

The study aims for inclusive enrollment by incorporating only inclusion criteria common for observational studies, with minimal exclusion criteria. To address potential biases and confounding, the main analysis population for the study will be further limited to individuals who are prospectively enrolled (prior to pregnancy outcome), not exposed to known teratogens and/or investigational medications during pregnancy, not exposed to other GLP-1 RA therapies during pregnancy or within 5-times the half-life of the drug prior to conception, not lost to follow-up, and not already included in the analysis population for a prior pregnancy. The definitions of the main analysis population and the rationale are provided in Section 9.11.1.1.

^a Time to product elimination (5 times terminal half-life); tirzepatide half-life = 5 days; therefore, time to elimination = 25 days

^b If a participant is exposed to the product during this period, they will be considered exposed during pregnancy

^c Participants may be retrospectively enrolled into the registry up to one year after pregnancy outcome but will not be included in main analysis

Figure 9.1. Study flow chart.

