9.7. Variables

9.7.1. Exposure Definitions and Ascertainment

Exposure to tirzepatide is a condition for inclusion into the exposed cohort. Exposure is defined as bodily uptake of any dose of tirzepatide at any time during pregnancy (from conception to pregnancy outcome) or prior to pregnancy (within a specified time based on the product's half-life). Due to the half-life of tirzepatide (approximately 5 days), tirzepatide is likely to be eliminated from the body within 5 half-lives (25 days or 3.5 weeks). Therefore, individuals exposed to tirzepatide within ≤ 25 days of DOC will be considered exposed. Individuals in the tirzepatide cohort who are exposed to other GLP-1 RA therapies during pregnancy or within 5 times the half-life of the drug prior to conception will be excluded from the main analysis to prevent class effect interactions. However, they may still be enrolled into the study as part of the tirzepatide exposed cohort.

Exposure to comparator products for weight management is defined as bodily uptake of any dose of a qualifying product for weight management at any time during pregnancy (from conception to pregnancy outcome) or prior to pregnancy (within 5-half-lives of DOC). Detailed information on drugs for weight management and their respective exposure windows are detailed in Drugs of Interest for Cohort Eligibility.

Detailed information on dose, route, frequency, dates/duration of exposure, and indication/reason for use will be collected, and exposure will be further categorized by earliest trimester of exposure. Section 9.7.5 provides information on the methods used to determine gestational age and trimester of exposure.

Exposure information will be updated at each pregnancy follow-up and changing exposures will be accounted for in the analysis. For example, if a pregnant individual was enrolled into the comparator cohort but later during pregnancy became exposed to tirzepatide, for the analysis they would be included in the tirzepatide exposed cohort.

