DOC, defined as 2^{0/7} gestational weeks, will be calculated as first day of LMP plus 14 days (2 weeks).

If EDD is not reported by the HCP but LMP data are available, the registry will use first day of LMP to calculate EDD, gestational age, and DOC.

Individuals will be considered exposed during pregnancy if the exposure occurs any time from 25 days prior to the DOC to the pregnancy outcome. For the analysis of MCM, first trimester exposure will be defined as exposure from 5 times the product's half-life (i.e., 25 days for tirzepatide) prior to the DOC to 13^{6/7} gestational weeks.

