- Sensitivity analyses will also be conducted to assess the potential impact of missing data and/or unmeasured confounding (e.g., quantitative bias analysis to estimate the overall strength of potential unmeasured confounding required to nullify the estimated treatment effect or reverse the statistical inference).¹⁰⁸
- A sensitivity analysis will be conducted that limits the tirzepatide exposed and the AOM active comparator cohorts to individuals with a diagnosis of obesity, or overweight with at least one weight-related comorbid condition at the time of conception.
- A sensitivity analysis will be conducted that expands the tirzepatide exposed cohort to individuals exposed to any other weight loss medications (including GLP-1 RAs) other than tirzepatide.
- In the main analysis, maternal use of within 5 half-lives of the respective medication is defined as a potential fetal exposure to medication use during pregnancy. This is a conservative estimate which may dilute a potential association between medication and the study outcomes. Sensitivity analysis will be conducted with shorter half-lives (i.e., 1-, 2- and 3-times half-lives) to define fetal exposure to medication use during pregnancy.
- Pregnant individuals who are exposed to a known teratogen or an investigational medication during or prior to pregnancy will be excluded from the main analysis population and described in the supplementary analyses. In the case that there are more than 10% of pregnant individuals with teratogen exposure during or prior to pregnancy, an additional sensitivity analysis will be considered by retaining those individuals in the analysis and addressing potential impact of teratogen exposure via analytical adjustment. More details will be included in the SAP.

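### Table 9.7 opens the exposure window for spontaneous abortion and preterm birth at conception, in conflict with the 5-half-life exposure rule and with the text of its own rows

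*Protocol*

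**What the plan says.** The general rule appears in several places. Section 9.7.1: "individuals exposed to tirzepatide within ≤ 25 days of DOC will be considered exposed". Section 9.7.5: "Individuals will be considered exposed during pregnancy if the exposure occurs any time from 25 days prior to the DOC to the pregnancy outcome". The Figure 9.1 notes in Section 9.5.2 give the basis: "tirzepatide half-life = 5 days; therefore, time to elimination = 25 days". The abstract and Table 9.1 footnote b say the same. For malformations, Section 9.7.5 writes the preconception days into the first-trimester window: "i.e., 25 days for tirzepatide) prior to the DOC to" 13 6/7 weeks. Section 9.11.2.7 ties the rule to the main analysis: "In the main analysis, maternal use of within 5 half-lives of the respective medication is defined as a potential fetal exposure". It then plans sensitivity analyses at 1, 2 and 3 half-lives.

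Table 9.7 (Section 9.11.2.2) puts an exposure window in brackets beside each outcome. Two of them start at conception: "SAB [Exposure: DOC to" 19 6/7 weeks, and "Preterm birth [Exposure: DOC to < 37 weeks gestation". The other rows that state a window say any trimester. In the spontaneous abortion (SAB) row, the numerator and denominator cover "individuals with pregnancy outcome data who are enrolled (and exposed, if applicable) prior to 20 gestational weeks". The preterm row has the same construction with 37 weeks. The notes under the table restate the 20- and 37-week limits for enrollment. Neither the rows nor the notes give a reason for a later start.

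**The concern.** Take a woman whose last dose was 10 days before DOC. By Sections 9.7.1 and 9.7.5 she belongs to the tirzepatide cohort, and she counts in the malformation analysis. By the two brackets she lies outside the window for SAB and preterm birth. Table 9.1 excludes anyone exposed to tirzepatide within 5 half-lives from both comparator cohorts, so she cannot move there. For these two outcomes she would be in no group.

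At stake is whether the exposed group is the same set of women from one outcome to the next, and whether two programmers working from the same table row would build the same group.

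**Working it through.** **1. The general window.** 5 half-lives × 5 days = 25 days, which reproduces the plan's figure. DOC is LMP + 14 days (Section 9.7.5), so the window opens at 14 − 25 = −11, that is, 11 days before LMP.

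**2. The windows side by side (tirzepatide).**

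| Source | Window opens |
|---|---|
| 9.7.1, 9.7.5 general rule; 9.11.2.7 main analysis | DOC − 25 days |
| 9.7.5, malformations | DOC − 25 days |
| Table 9.7, SAB and preterm birth, bracket | DOC |
| Table 9.7, SAB and preterm birth, numerator and denominator | no lower limit |
| Table 9.7, any-trimester rows, read literally | LMP = DOC − 14 days |

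The two brackets open 25 days later than the general rule. The any-trimester rows, read literally, also miss DOC − 25 to DOC − 15, which is 25 − 14 = 11 days.

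**3. The half-life sensitivity analyses.** Section 9.11.2.7 presents 1, 2 and 3 half-lives as shorter alternatives to the main rule: 5, 10 and 15 days before DOC against 25. With a bracket that opens at DOC, the main window has 0 preconception days, so all three alternatives would be wider than the main analysis they are meant to tighten.

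**4. Effect on power.** The share of exposed women with preconception-only dosing is not in the documents, so it is varied here.

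Inputs from Section 9.9.1 and Table 9.4: two-sided α 0.05, power 80%, 1:1 allocation, SAB 11.8%, preterm birth 8.47%, 364 enrolled and 265 live births per cohort. The method is the Walters arcsine approximation to Fisher's exact test, with n1, p1 for the comparator and n2, p2 for the exposed group:

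power = Φ( √(4·n1·n2/(n1+n2)) × [asin√(p2 − 1/(2·n2)) − asin√(p1 + 1/(2·n1))] − 1.96 )

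At a relative risk (RR) of 3 this gives 265 per cohort for malformations, 57 for SAB and 85 for preterm birth, all as in Table 9.4.

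Starting sizes: SAB 364 × 0.9 ≈ 328 analysable women; preterm birth 265 live births. Both are approximate, since Table 9.7 restricts these denominators further. The comparator is held at full size.

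| Exposed share dropped | SAB exposed n | Power RR 2 | Power RR 3 | Preterm exposed n | Power RR 2 | Power RR 3 |
|---|---|---|---|---|---|---|
| 0% | 328 | 97% | >99% | 265 | 81% | >99% |
| 10% | 295 | 97% | >99% | 238 | 79% | >99% |
| 25% | 246 | 95% | >99% | 199 | 74% | >99% |
| 50% | 164 | 88% | >99% | 132 | 62% | 99% |
| 75% | 82 | 66% | 99% | 66 | 39% | 90% |

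At the RR of 3 used for planning, little is lost. At RR 2, preterm birth would lose power noticeably if a large share were dropped.

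**The case against.** The strongest reply is that nobody need be dropped. The numerator and denominator text asks only for exposure before 20 or 37 weeks, and a dose 10 days before DOC meets that. The notes under the table limit enrollment, not the start of exposure. Sections 9.7.5 and 9.11.2.7 make no exception for SAB or preterm birth. This stands as far as it goes: a reader might infer that the protocol definitely excludes these women, and it does not. It gives two instructions that disagree. The bracket is the only lower limit in these rows, and the column is labelled as the exposure window, so it cannot be dismissed as decoration.

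One could also read a DOC start as the period of fetal exposure, which residual drug from a late preconception dose would enter. Nothing in the protocol says the bracket means that, and Section 9.7.1 defines exposure by when a dose is taken up.

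A reader might also infer that these two rows alone are out of line. Read literally, the any-trimester rows miss part of the preconception period too. The difference is that the general definition can be read into a generic phrase, but not into an explicit DOC start.

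Finally, the outcomes are secondary with nominal p-values (Section 9.11.2), and enrollment after pregnancy recognition already left-truncates early losses (Section 9.13). Both points limit the weight of the finding. Neither removes the conflict.

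**Conclusion.** The conflict is real and confined to two secondary outcomes. Table 9.7 states a start at DOC for SAB and preterm birth that disagrees with Sections 9.7.1, 9.7.5 and 9.11.2.7 and with the rows' own text. If the bracket is applied, women with preconception-only exposure are in no cohort for these outcomes and the half-life sensitivity analyses lose their sense. If the row text is applied, they stay in.

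The number of women affected cannot be derived. One might be tempted to spread last doses evenly from 25 days before DOC to w days after, so that the share is 25/(25 + w): 64%, 47% or 37% for w of 14, 28 or 42 days. Neither the even spread nor w comes from the protocol, so these figures are not evidence of the loss. Section 7.4.3 says patients are advised to stop when pregnancy is recognized; dosing up to recognition would make the share smaller, but no figure follows from that either.

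Given the power results, the harm is not a failed comparison at RR 3. It is an exposed population that may differ between outcomes without a stated reason, so that SAB and preterm results could not be read alongside the malformation results as describing the same women. It should be corrected, but it does not threaten the primary analysis.

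**What to change.** In Table 9.7, change the SAB bracket to run from 5 half-lives before DOC to 19 6/7 weeks, and the preterm bracket from 5 half-lives before DOC to <37 weeks. Stating the limit in half-lives rather than as 25 days also serves the active comparators, whose windows Section 9.7.1 sets product by product. Add one table note that any trimester includes the 5-half-life preconception period, so that the remaining rows are aligned with Section 9.7.5 as well. Keep the 1-, 2- and 3-half-life sensitivity analyses.

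If a DOC start is intended for these outcomes, give the reason, make the numerator and denominator text match it, and restate what the half-life sensitivity analyses mean for them.

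The cost is two table entries and one note, with no change to data collection or sample size.
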